6.1.1 Serious Adverse Event Collection and Reporting

Sections 5.5.1 in the Investigator Brochure (IB) represent the Reference Safety Information to determine expectedness of serious adverse events for expedited reporting. Following the subject's written consent to participate in the study, all SAEs, whether related or not related to study drug, must be collected, including those thought to be associated with protocol-specified procedures. All SAEs must be collected that occur during the screening period and within 84 days of discontinuation of dosing. If applicable, SAEs must be collected that relate to any later protocol-specified procedure (eg, a follow-up skin biopsy).

The investigator must report any SAE that occurs after these time periods and that is believed to be related to study drug or protocol-specified procedure.

An SAE report must be completed for any event where doubt exists regarding its seriousness.

If the investigator believes that an SAE is not related to study drug, but is potentially related to the conditions of the study (such as withdrawal of previous therapy or a complication of a study procedure), the relationship must be specified in the narrative section of the SAE Report Form.

SAEs, whether related or not related to study drug, and pregnancies must be reported to Sponsor or designee within 24 hours of awareness of the event. SAEs must be recorded on the SAE Report Form; pregnancies on a Pregnancy Surveillance Form (electronic or paper forms). The preferred method for SAE data reporting collection is through the eCRF. The paper SAE/pregnancy surveillance forms are only intended as a back-up option when the eCRF system is not functioning. In this case, the paper forms are to be transmitted via email or confirmed facsimile (fax) transmission to:

SAE Email Address: Refer to Contact Information list.

SAE Facsimile Number: Refer to Contact Information list.

For studies capturing SAEs through electronic data capture (EDC), electronic submission is the required method for reporting. In the event the electronic system is unavailable for transmission, paper forms must be used and submitted immediately. When paper forms are used, the original paper forms are to remain on site.

SAE Telephone Contact (required for SAE and pregnancy reporting): Refer to Contact Information list.

If only limited information is initially available, follow-up reports are required. (Note: Follow-up SAE reports must include the same investigator term(s) initially reported.)

If an ongoing SAE changes in its intensity or relationship to study drug or if new information becomes available, the SAE report must be updated and submitted within 24 hours to Sponsor or designee using the same procedure used for transmitting the initial SAE report.

All SAEs must be followed to resolution or stabilization.

BMS will be reporting adverse events to regulatory authorities and ethics committees according to local applicable laws including European Directive 2001/20/EC and FDA Code of Federal Regulations 21 CFR Parts 312 and 320. A SUSAR (Suspected, Unexpected Serious Adverse Reaction) is a subset of SAEs and will be reported to the appropriate regulatory authorities and investigators following local and global guidelines and requirements.

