3.5 Discontinuation of Study Therapy

Subjects who discontinue treatment with investigational product during the Double-Blind Treatment Period must continue to be assessed for all efficacy measures and for safety at all remaining double-blind study visits through Week 24 (Day 169) (see [Table 5.1-2](#)). Those subjects who discontinue treatment with the study drug during the double-blind period will also require visits to assess safety and immunogenicity at 28 and 84 days after the last dose of study drug. If these visits fall within ± 14 days of a scheduled double-blind study visit, only an additional laboratory assessment (immunogenicity) needs to be performed at the scheduled study visit. Otherwise, the follow-up visits need to be performed.

Subjects who discontinue study drug during the Open-Label Treatment period should comply with protocol specified follow-up procedures as outlined in [Section 5](#). The only exception to this requirement is when a subject withdraws consent for all study procedures including post-treatment study follow-up or loses the ability to consent freely (ie, is imprisoned or involuntarily incarcerated for the treatment of either a psychiatric or physical illness).

Subjects MUST discontinue investigational product (and non-investigational product at the discretion of the investigator) for any of the following reasons:

- Subject's request to stop study treatment
- Any clinical adverse event (AE), laboratory abnormality or intercurrent illness which, in the opinion of the investigator, indicates that continuation of study therapy is not in the best interest of the subject
- Pregnancy
- Missed Doses:
 - During the double-blind period, any subject who misses greater than four consecutive doses or greater than eight total doses must be discontinued from study therapy
 - During the open-label period, any subject who misses greater than six consecutive doses or greater than ten total doses must be withdrawn from the study
- Significant non-compliance with protocol (ie, procedures, assessments, medication, etc). The investigator should discuss such issues with the BMS Medical Monitor.
- Use of prohibited medication. The investigator should discuss the use of a prohibited medication with the Medical Monitor prior to withdrawing a subject from study therapy

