5.1.2 Order of Study Assessments

It is strongly encouraged that study assessments be performed in the following order:

- 1) Patient reported outcomes (PROs) questionnaires
- 2) Salivary Flow
 - a) Unstimulated salivary flow
 - b) Stimulated salivary flow
- 3) Ophthalmologic Assessments - there is a ± 5 day window for the completion of these assessments
 - a) Schirmer test

- b) Tear break-up time
- c) Ocular staining
- 4) AE collection
- 5) Vital signs
- 6) Joint assessments
- 7) Investigator assessments
- 8) Blood draws
- 9) Study Drug Administration

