- The mean change from baseline in patient symptoms using the Numeric Rating Scale (NRS) for eye dryness at all measured time points up to Day 169.
- The mean change from baseline in subject assessment of disease activity at all measured time points up to Day 169.
- The mean change from baseline in the physician global assessment of disease activity at all measured time points up to Day 169.
- The mean change from baseline in patient fatigue using PROMIS Fatigue assessment at all measured time points up to Day 169.
- The mean change from baseline in female sexual function using the FSFI at all measured time points up to Day 169.
- The mean change from baseline in patient function using SF-36 at all measured time points up to Day 169.
- Geometric mean of trough concentration (C_{min}) of abatacept at all measured time points.
- Proportion of subjects with at least one positive immunogenicity response up to Day 169 and during 3 months follow up (for subjects who discontinue during the 6-months double-blind)

and during the cumulative abatacept period and 3 months follow-up (for the cumulative abatacept population).

- Safety (proportion of subjects with adverse events, deaths, SAEs, and AEs leading to discontinuation and proportion of laboratory marked abnormalities) up to Day 169 and during the cumulative abatacept period and follow-up period.

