8.4.3 Safety Analyses

The proportion (%) of subjects with adverse events, deaths, SAEs, and AEs leading to discontinuation and subjects with laboratory marked abnormalities up to start of open label for subjects continuing in the OL or up to last dosing date +56 days for subjects discontinuing during double blind will be provided per treatment group using the as-treated population. These safety endpoints will also be summarized during the cumulative abatacept period (from the first day of abatacept treatment in the study up to 56 days after the last abatacept treatment in the study) for the cumulative abatacept population. For the cumulative abatacept population all subjects will be combined in one group.

The proportion (%) of subjects with at least one positive immunogenicity response (relative to baseline) up to Day 169 and 3 months follow up (for subjects who discontinue in the Day 169 short-term period) and during the cumulative abatacept period and 3 months follow-up (for the cumulative abatacept population) will be summarized using the immunogenicity population.

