At the end of the double blind treatment period there will be a 197 day open label extension (OLE). On Day 169 all subjects continuing on treatment (including those subjects who received placebo during the double blind period) will receive open-label abatacept SC, 125mg weekly to Day 357. Subjects not wishing to continue on open-label abatacept have the option of discontinuing treatment at the end of the Double-Blind Period and proceeding to the post-treatment follow-up period. Study procedures will occur as specified in protocol Table 5.1-3.

Follow-Up Period:

Subjects who discontinue treatment of study drug during the double-blind or open-label periods or complete the study will have three follow-up visits 28, 85 and 169 days after the last treatment visit, to perform safety and laboratory assessments, including immunogenicity testing. Subjects who go into the post-study drug access program (i.e. switch from study drug to post-study abatacept) will be excluded from the Follow-up period.

The study design schematic is presented in Figure 2.1-1. On office visit days, SC injections should occur after all assessments (including efficacy, AE, blood draws for assessment of immunogenicity and drug concentrations) are done.

Figure 2.1-1: Study Design Schematic

The approximate duration of the study is up to a 4-week screening period (28 days), a 24-week Double-Blind Period (169 days), a 197-day open label abatacept period and a subsequent 24 week follow up period (169 days), for a total of approximately 80 weeks (561 days).

The start of the trial is defined as the date the first subject signs the informed consent. End of trial is defined as the last visit or scheduled procedure shown in the Time & Events schedule for the last subject. The study will continue beyond primary endpoint collection until the End of Trial.

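### Mandatory collection of all SAEs ends 84 days after dosing stops, which is before Day 169 for anyone whose last dose is before Day 85, yet the SAE endpoint runs to Day 169

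*Protocol*

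**What the plan says.** **Collection.** Protocol 6.1.1 first sets a general rule from the time of consent: "all SAEs, whether related or not related to study drug, must be collected, including those thought to be associated with protocol-specified procedures". That sentence has no end date. The next one sets limits: "All SAEs must be collected that occur during the screening period and within 84 days of discontinuation of dosing". For anything later, "The investigator must report any SAE that occurs after these time periods and that is believed to be related to study drug" or to a protocol procedure.

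**Visits.** Under Protocol 3.5, subjects who stop drug in the double-blind period "must continue to be assessed for all efficacy measures and for safety at all remaining double-blind study visits through Week 24 (Day 169"). Protocol 3.1 says the same. The visit order in Protocol 5.1.2 includes "4) AE collection".

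**Endpoint.** Protocol 8.3.2 lists "Safety (proportion of subjects with adverse events, deaths, SAEs, and AEs leading to discontinuation and proportion of laboratory marked abnormalities) up to Day 169", and also covers the cumulative abatacept and follow-up periods.

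**Analysis.** Protocol 8.4.3 counts events "up to last dosing date +56 days for subjects discontinuing during double blind". SAP 6.1 and 7.6 use the same 56 days, or the first open-label dose if that is earlier.

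**The concern.** Four parts of the plan set a time limit on safety for a subject who stops drug early, and they do not agree. Visits and the endpoint run to Day 169, all-cause SAE collection runs to last dose + 84 days, and the tables run to last dose + 56 days. The 84-day limit matches the last post-dose visit in Protocol 3.1.4, so it suits subjects who finish treatment. For early stoppers the last visit can fall well after it. The follow-up table (Table 5.1-6, footnote a) adds that their separate post-dose visits may not be needed, so the double-blind visits may be their only contacts.

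The Day 169 SAE endpoint is at stake. Within the gap, whether an SAE is recorded may depend on stopping drug, which happens after randomisation, and on an investigator's opinion of causality. A randomised safety comparison is meant to avoid both. An analysis window can be widened later, but an SAE that was never collected may not be recoverable. The SAP already plans efficacy sensitivity analyses using off-treatment data to Day 169 (7.1.5). A matching SAE summary would rest on collection that the protocol does not clearly require.

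**Working it through.** The plan gives no figure of its own to reproduce, so the check is day arithmetic.

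**Inputs**
- Weekly dosing (Protocol 3.1.2): 24 double-blind dose days, Days 1, 8, ..., 162.
- Endpoint and last double-blind visit: Day 169 (Protocol 8.3.2 and 3.5).
- All-cause SAE window: w = 84 days (Protocol 6.1.1).
- Analysis window for discontinuers: w = 56 days (Protocol 8.4.3; SAP 6.1 and 7.6).
- Assumption: discontinuation of dosing means the day of the last dose, d.

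**Formula.** The window closes on Day d + w. The gap to Day 169 is 169 − (d + w), which is positive when d < 169 − w.

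- w = 84: gap when d < 85, that is dose days 1 to 78, or 12 of 24.
- w = 56: gap when d < 113, that is dose days 1 to 106, or 16 of 24.

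| Last dose (day) | All-SAE window closes | Gap to Day 169 | Analysis window closes | Gap to Day 169 |
|---|---|---|---|---|
| 1 | 85 | 84 | 57 | 112 |
| 29 | 113 | 56 | 85 | 84 |
| 57 | 141 | 28 | 113 | 56 |
| 78 | 162 | 7 | 134 | 35 |
| 85 | 169 | 0 | 141 | 28 |
| 106 | 190 | none | 162 | 7 |
| 113 | 197 | none | 169 | 0 |

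The analysis window always closes 84 − 56 = 28 days before the collection window. Every SAE that the planned double-blind tables would count therefore falls inside the period of all-cause collection.

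**Example.** A subject takes the last dose on Day 29 and stays in the study. The all-cause window closes on Day 113. The Day 141 and Day 169 visits fall after it. An SAE on Day 150 judged unrelated is inside the endpoint in 8.3.2, outside the explicit collection rule in 6.1.1, and outside the table in 8.4.3.

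**Reading 6.1.1.** If the open-ended sentence governs, the 84-day sentence and the related-only rule after it have no function. If the 84-day sentence governs, the gap above is real. Sites could follow either reading.

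**After the fix.** With collection to the later of d + 84 and the last scheduled visit (Day 169 or later for a subject who remains in the study), the gap to Day 169 is 0 for every d.

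**The case against.** The strongest reply is that nothing planned is damaged. The double-blind safety tables stop at last dose + 56 days, so no planned randomised SAE comparison depends on a causality opinion, and lengthening collection alone would not change any of those tables. This stands. A reader might infer that the planned SAE proportions are incomplete or filtered by causality, and the documents do not support that. What remains is that the tables do not deliver the endpoint as 8.3.2 words it.

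A second reply is that collection does not stop. SAEs attributed to drug or procedure are still reportable, the general sentence in 6.1.1 is open-ended, and AE collection is a visit step. This also stands. It makes the defect an inconsistency and not a clear halt in collection, but it does not tell a site what to do with an unrelated SAE in the gap.

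A third is that an exposure-based window is coherent. Protocol 3.3.1 puts five half-lives at 70 days, and 84 days exceeds that. This is fair for drug-related risk. It does not bring the window into line with an endpoint and visits fixed at Day 169.

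Finally, a reader might extend the gap to everyone, because under the SAP subjects "will have three follow-up visits 28, 85 and 169 days after the last treatment visit". The documents do not support that. The supplied protocol's follow-up ends at 84 days, matching its SAE window. The SAP reflects later amendments, and the SAE window in force with its longer follow-up is not in the documents. The SAP also excludes from follow-up those who move to post-study abatacept. The 84-day figure may itself have been superseded.

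**Conclusion.** The point holds as an internal inconsistency of modest size. In the supplied protocol, the explicit duty to collect all SAEs regardless of causality closes before Day 169 for a last dose before Day 85, by 7 to 84 days on the weekly schedule. The rule therefore cannot be relied on to deliver the Day 169 SAE endpoint for early stoppers who are still attending visits. Separately, the 56-day analysis window falls short of that endpoint for last doses before Day 113, by 7 to 112 days.

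This rests on the last dose marking the end of dosing; if the later date of the decision to stop counts, the gap shrinks. It applies only to subjects who remain under follow-up. The documents give neither the number of early stoppers nor an SAE rate, so the number of SAEs affected cannot be computed. They also do not show that early stoppers leave mainly for tolerability, and the point does not need it.

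**What to change.** 1. In Protocol 6.1.1, replace the 84-day sentence with a rule to collect all SAEs, related or not, from consent to the later of 84 days after the last dose and the subject's last scheduled study visit. Keep related-only reporting for events after that. This removes the ambiguity and also works with whichever follow-up length is in force.
2. Reconcile the Day 169 endpoint in 8.3.2 with the 56-day window in Protocol 8.4.3 and SAP 6.1 and 7.6. One way is to keep the 56-day tables and add a summary of SAEs and deaths to Day 169, before any open-label dose, by randomised arm.
3. Check the SAE window in the current protocol amendment against the follow-up length in the SAP.

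The cost is one protocol sentence with matching CRF guidance, a few more SAE reports and one more table. No visit is added. The first change alone would leave the planned tables as they are, so the first two belong together.

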6.2 Nonserious Adverse Events

A *nonserious adverse event* is an AE not classified as serious.

6.2.1 Nonserious Adverse Event Collection and Reporting

The collection of nonserious AE information should begin at initiation of study drug. Nonserious AE information should also be collected from the start of a placebo lead-in period or other observational period intended to establish a baseline status for the subjects.

Nonserious AEs should be followed to resolution or stabilization, or reported as SAEs if they become serious (see [Section 6.1.1](#)). Follow-up is also required for nonserious AEs that cause interruption or discontinuation of study drug and for those present at the end of study treatment as appropriate. All identified nonserious AEs must be recorded and described on the nonserious AE page of the CRF (paper or electronic).

Completion of supplemental CRFs may be requested for AEs and/or laboratory abnormalities that are reported/identified during the course of the study.

6.3 Laboratory Test Result Abnormalities

The following laboratory test result abnormalities should be captured on the nonserious AE CRF page or SAE Report Form (electronic) as appropriate. Paper forms are only intended as a back-up option when the electronic system is not functioning.

- Any laboratory test result that is clinically significant or meets the definition of an SAE
- Any laboratory test result abnormality that required the subject to have study drug discontinued or interrupted
- Any laboratory test result abnormality that required the subject to receive specific corrective therapy

It is expected that wherever possible, the clinical rather than laboratory term would be used by the reporting investigator (eg, anemia versus low hemoglobin value).

6.4 Pregnancy

If, following initiation of the study drug, it is subsequently discovered that a study subject is pregnant or may have been pregnant at the time of study exposure, including during at least 5 half lives after product administration, the investigator must immediately notify the Sponsor or designee of this event and complete and forward a Pregnancy Surveillance Form to BMS Designee within 24 hours of awareness of the event and in accordance with SAE reporting procedures described in [Section 6.1.1](#).

In most cases, the study drug will be permanently discontinued in an appropriate manner (eg, dose tapering if necessary for subject safety). Please call the Sponsor or designee within 24 hours of awareness of the pregnancy.

Protocol-required procedures for study discontinuation and follow-up must be performed on the subject.

The investigator must immediately notify the Sponsor or designee of this event and complete and forward a Pregnancy Surveillance Form to Sponsor or designee within 24 hours of awareness of the event and in accordance with SAE reporting procedures described in [Section 6.1.1](#).

Follow-up information regarding the course of the pregnancy, including perinatal and neonatal outcome and, where applicable, offspring information must be reported on the Pregnancy Surveillance Form.

Any pregnancy that occurs in a female partner of a male study participant should be reported to Sponsor or designee. In order for BMS to collect any pregnancy surveillance information from the female partner, the female partner must sign an informed consent form for disclosure of this information. Information on this pregnancy will be collected on the Pregnancy Surveillance Form.

6.5 Overdose

An overdose is defined as the accidental or intentional administration of any dose of a product that is considered both excessive and medically important. All occurrences of overdose must be reported as an SAE (see [Section 6.1.1](#) for reporting details.).

6.6 Potential Drug Induced Liver Injury (DILI)

Specific criteria for identifying potential DILI have not been identified for this protocol. Standard medical practice in identifying and monitoring hepatic issues should be followed.

6.7 Other Safety Considerations

Any significant worsening noted during interim or final physical examinations, electrocardiogram, x-ray filming, or any other potential safety assessment required or not required by protocol, should also be recorded as a nonserious or serious AE, as appropriate, and reported accordingly.

7 DATA MONITORING COMMITTEE AND OTHER EXTERNAL COMMITTEES

Data Monitoring Committee (DMC) will be instituted to perform safety monitoring oversight.

Details will be contained in the DMC Charter.

8 STATISTICAL CONSIDERATIONS

8.1 Sample Size Determination

A hierarchical testing procedure will be applied for the primary endpoint (change from baseline in ESSDAI at Day 169) and the 2 key secondary endpoints (change from baseline in ESSPRI at Day 169 and change from baseline in the stimulated whole salivary flow at Day 169) to ensure the preservation of the overall type I error of 5%. The first key secondary endpoint will only be tested (at a significance level of 5%) if the test for the primary endpoint is statistically significant at a significance level of 5%. If both the test for the primary endpoint and the first key secondary endpoint are statistically significant (both at a significance level of 5%), then the second key secondary endpoint will be tested (at a significance level of 5%).

A sample size of 172 patients (86 per arm) will achieve 98% power to detect a treatment difference of 3 in changes from baseline in ESSDAI at Day 169 between the abatacept and placebo group using a two-sided t-test with a significance level (alpha) of 0.05 and assuming a common SD of 4.8. The sample size of 86 patients per arm will achieve 90% power to detect a treatment difference of 1 in change from baseline in ESSPRI at Day 169 assuming a common SD of 2. Taking into account the hierarchical procedure, a sample size of 86 patients per arm will achieve an overall power of at least 88.2% (98% multiplied by 90%) to detect both a treatment difference of 3 in mean change from baseline in ESSDAI and a difference of 1 in change from baseline in ESSPRI at Week 24 (Day 169).

The treatment differences of 3 for ESSDAI and 1 for ESSPRI correspond to the minimal clinically important improvement (MCII) for ESSDAI and ESSPRI³⁶, the key endpoints that address the major signs and symptoms of this disease. Estimates of the SD of mean change from baseline in ESSDAI derived from published results³⁷, range from 3.6 to 6.3. Estimates of the SD of mean change from baseline in ESSPRI derived from published results range from 1.7 to 2.2.³⁸

In addition, the power to detect a treatment difference in mean change from baseline of 0.165 mL/min in salivary flow (approximately similar to median reported increase/min with abatacept by Adler et al⁴) in subjects with stimulated whole salivary flow at baseline of at least 0.1 mL/min is 91%, assuming a SD of 0.275 and for a sample size of 62 subjects per arm with a residual salivary flow of at least 0.1 mL/min at screening and baseline.⁴ Taking into account the hierarchical procedure, a sample size of 86 patients per arm will achieve an overall power of at least 80.3 % (98% multiplied by 90% multiplied by 91%) to detect a treatment difference of 3 in mean change from baseline in ESSDAI, a difference of 1 in mean change from baseline in ESSPRI and a treatment difference of 0.165 mL/min in mean change from baseline in salivary flow(in subjects with stimulated whole salivary flow at screening and at baseline of at least 0.1 mL/min) at Week 24 (Day 169).

